7.2 Method of Evaluation

7.2.1 Efficacy Evaluation

7.2.1.1 Investigator's Global Assessment (IGA)

The investigator or subinvestigator will score the severity (0 = clear, 1 = almost clear, 2 = mild, 3 = moderate, 4 = severe/very severe) of systemic symptoms (erythema, infiltration, papules, effusion [liquid], and scab formation).⁵ The result will be recorded in the source document and CRF. The same subject will be evaluated by the same dermatologist, as much as possible.

Symptom	Severity score
No inflammatory signs of AD	0 = Clear
Just perceptible erythema and just perceptible papulation/infiltration	1 = Almost clear
Mild erythema and mild papulation/infiltration	2 = Mild
Moderate erythema and moderate papulation/infiltration	3 = Moderate
Severe erythema and severe papulation/infiltration with oozing/crusting	4 = Severe/very severe

7.2.1.2 Eczema Area and Severity Index (EASI)

The investigator or subinvestigator will score the severity (0-3 points) and BSA (0-6 points) based on the 4 symptoms (erythema, infiltration/papules, excoriation, and lichenification) on the 4 body regions (face, neck, and head; upper limbs; trunk; and lower limbs) and record the results in the source document and CRF.⁶ As shown in the table below, the score of each region will be calculated and totalized. The maximum EASI score is 72 points. The same subject will be evaluated by the same dermatologist, as much as possible.

Body region	Calculation of the score for each region
Face, neck, and head	$(E + I + Ex + L) \times \text{score of BSA} \times 0.1$
Upper limbs	$(E + I + Ex + L) \times \text{score of BSA} \times 0.2$
Trunk	$(E + I + Ex + L) \times \text{score of BSA} \times 0.3$
Lower limbs	$(E + I + Ex + L) \times \text{score of BSA} \times 0.4$

E = severity score of erythema; I = severity score of infiltration/papules; Ex = severity score of excoriation; L = severity score of lichenification

Severity score: clear = 0; slight = 0.5; mild = 1; mild-moderate = 1.5; moderate = 2; severe = 2.5; very severe = 3

Score of BSA: clear = 0; 1% to 9% = 1; 10% to 29% = 2; 30% to 49% = 3; 50% to 69% = 4; 70% to 89% = 5; 90% to 100% = 6

7.2.1.3 Visual Analogue Scale (VAS) for Pruritus

The investigator or subinvestigator will evaluate the level of pruritus based on VAS⁷. The subjects will mark the point of pruritus intensity during the last 24 hours on the line of a 100-mm VAS sheet (Appendix 2) between the left end (no pruritus) and the right end (very severe pruritus). The investigator or subinvestigator will record the length from the left end to the mark (integer value with mm as unit) in the medical record and CRF. The VAS sheet will be kept as the source document.

7.2.1.4 Verbal Rating Scale (VRS) for Pruritus

The investigator or subinvestigator will evaluate the pruritus intensity based on VRS⁷.

The subjects will evaluate the pruritus intensity according to the following criteria.

The subjects will record the level of pruritus, and the time and date of evaluation in a pruritus diary.

0: None

1: Mild

2: Moderate

3: Severe

The investigator or subinvestigator will record details of the pruritus diary in the CRF. The pruritus diary will be kept as the source document.

7.2.1.5 Dermatology Life Quality Index (DLQI)

The investigator or subinvestigator will evaluate the effect of OPA-15406 on daily life according to the DLQI⁸ (Appendix 3). The subjects will answer 10 questions about the effects of the symptoms on their daily life. The investigator or subinvestigator will record the results in the source document and CRF. The total DLQI score is 30 points at the most.

7.2.1.6 Patient-Oriented Eczema Measure (POEM)

The investigator or subinvestigator will evaluate eczema according to the POEM⁹ (Appendix 4). The subjects will answer 7 questions about their eczema. The investigator or subinvestigator will record the results in the source document and CRF. The total score of POEM is 28 points at the most.

7.2.1.7 Affected BSA

The investigator or subinvestigator will draw the affected BSA (range of skin eruption at the time of examination) on the human body drawing (Appendix 5) to determine the affected areas (%) on the respective 4 body regions (head, face, and neck; upper limbs; trunk; and lower limbs). The respective affected areas (%) will be recorded in the source document and CRF. One palm of the subject corresponds to 1% BSA.

7.2.2 Safety Evaluation

7.2.2.1 Physical Examination

The investigator or subinvestigator will assess the subject's physical condition by interview, visual examination, or palpation.

7.2.2.2 Vital Signs (Including Body Weight)

After the subject has rested for 3 minutes or more in a sitting position, body temperature (measured by 0.1°C in the armpit), blood pressure (systolic/diastolic), pulse rate, and body weight (unit in kg; rounded to one decimal place) will be measured, and the results of measurement will be recorded in the source document and CRF.

7.2.2.3 Clinical Laboratory Tests

The investigator or subinvestigator will perform clinical laboratory tests for the following items. Date of blood and urine sampling will be recorded on the source document and CRF.

- Hematology: differential white blood cell count (neutrophils, lymphocytes, monocytes, eosinophils, basophils), white blood cell count, red blood cell count, hemoglobin, hematocrit, platelets
- Serum chemistry: total cholesterol, total protein, albumin, BUN, creatinine, total bilirubin, AST (GOT), ALT (GPT), γ -GTP, LDH, ALP, serum electrolytes (Ca, Na, K, Cl)
- Qualitative urinalysis: glucose, protein

The tests will be performed at the central laboratory. The investigator or subinvestigator will confirm the tests results from the central laboratory, put the date and his or her printed name and personal seal or signature on the report from the clinical laboratory, and retain it for each subject as the source document. The central laboratory will send the tests results to the sponsor (in the form of electronic data).

7.2.2.4 12-Lead ECG

After the subject has rested for at least 10 minutes in a supine position, an ECG will be obtained. The ECG recording should be completed before blood sampling, as much as possible. For the ECG measurement, heart rate, RR interval, PR interval, QRS interval, QT interval, and QTc interval will be measured, using a 12-lead electrocardiograph obtained from the central ECG reading facility. The measurement results will be analyzed at the central ECG reading facility. The investigator or subinvestigator will confirm the “12-lead ECG analysis report” from the central ECG reading facility, assess whether the ECG result is normal or abnormal, and record the time and date of the measurement, assessment result, and findings in the source document and CRF. Then, the investigator or subinvestigator will put the confirmation date and his or her printed name and personal seal or signature on the “12-lead ECG analysis report” from the central ECG reading facility and retain it for each subject as the source document.

If it is necessary to allocate IMP before receiving the results from the central ECG reading facility, the automated analysis result from the 12-lead electrocardiograph at the screening examination (the same ECG data as that to be sent to the central ECG reading facility) can be used to determine the subject’s eligibility. In such cases, the investigator or subinvestigator will put the date of confirmation and his or her printed name and personal seal or signature on the automated analysis result and retain it as the source document.

The central ECG reading facility will send the 12-lead ECG analysis results (in electronic data format) to the sponsor.

7.2.3 Pharmacokinetics

Plasma OPA-15406 concentrations will be measured except for subjects in the vehicle group. On the day of blood sampling, the subjects will visit the trial site without morning IMP administration.

1) Blood sampling timepoints

Plasma trough concentration of OPA-15406 (prior to IMP administration at Week 1, Week 4, and Week 8 of IMP administration; all subjects)

Plasma concentration of OPA-15406 (prior to IMP administration and 2 hours, 4 hours, and 8 hours postdose on Day 1 and at Week 4. [however, prior to IMP administration at Week 4 is the same as trough concentration at Week 4]): specific trial sites (target of 6 subjects from each group)

2) Rationale for blood sampling timepoints

Timepoints are selected to confirm the drug concentration of OPA-15406 and the internal exposure to OPA-15406 in Japanese AD patients and to obtain comparable internal exposure data to those of the phase 2 trial outside Japan (271-12-205).

3) Method of blood sampling and processing

Sufficient caution should be taken for the parts of sterilization and site of blood sampling to avoid the blood samples from contamination with any IMP remnant on the skin surface. Approximately 5 mL of blood will be collected per dose from arm vein using vacuum blood collection tube (with heparin Na contained) and sufficiently mixed. The sample will be mixed by inversion and cooled in ice water, and it will be centrifuged at approximately 3000 rpm for 10 minutes within 30 minutes after blood sampling, and from which approximately the same amount of plasma will be promptly taken into two polypropylene tubes and stored frozen at -15°C or less. When a refrigerated centrifuge is available, the blood will be centrifuged at 4°C. For each subject, the time and date of latest IMP administration and blood sampling will be record on the source document and CRF.

4) Sending plasma samples

The contract research organization for clinical laboratory tests will send the samples divided into two tubes frozen on dry ice to the bioanalytical laboratory. The plasma concentration of OPA-15406 will be determined at the bioanalytical laboratory by using the liquid chromatography with tandem mass spectrometry (LC-MS/MS). The bioanalytical laboratory will measure samples of the OPA-15406 group according to the randomization table. Residual plasma samples after measurement will be stored at -15°C or less by the bioanalytical laboratory until the sponsor allows their disposal. The sponsor will report the completion of measurement to the bioanalytical laboratory. The bioanalytical laboratory will submit the report on results of drug concentration measurement (copy) and the measurement results (electronic data) to the sponsor.

7.2.4 Status of IMP Administration

Details of the administration diary will be recorded in the CRF. Administration status will be recorded as poor if the frequency of IMP administration is less than 80%.

7.2.5 Severity of AD

The investigator or subinvestigator will determine the severity¹⁰ (mild, moderate, severe, or very severe) and record the result in the source document and CRF.

Definition	Severity
Just mild skin eruption regardless of the area	Mild
Skin eruption with severe inflammation on <10% of the BSA	Moderate
Skin eruption with severe inflammation on ≥10% to <30% of the BSA	Severe
Skin eruption with severe inflammation on ≥30% of the BSA	Very severe

Mild skin eruption: lesions mainly consisting of mild erythema, dryness, or desquamation

Skin eruption with severe inflammation: lesions consisting of erythema, papules, erosion, infiltration, or lichenification

7.3 Measures to Be Taken for Subjects Visiting or Planning to Visit Other Hospitals or Departments

At the time of obtaining informed consent, the investigator or subinvestigator will confirm whether or not the subject is receiving treatment at another hospital or department. If the subject is receiving treatment at another hospital or department, the investigator or subinvestigator will inform the attending physician of that hospital or department about the subject's participation in the clinical trial and the IMP being used, with the subject's consent. The investigator or subinvestigator will also obtain and record in the CRF information on the treatment that the subject is receiving at the other hospital or department (name of disease being treated and information on the type of treatment or measures being implemented) and judge whether or not the subject should participate in the trial.

If a subject visits another hospital or department during the trial period, the investigator or subinvestigator will inform the attending physician of that hospital or department about the subject's participation in the clinical trial and the IMP being used. The investigator or subinvestigator will also obtain and record in the CRF information on the treatment that the subject receives at the other hospital or department (name of disease treated and information on the type of treatment or measures implemented) and judge whether or not the subject should continue to participate in the trial.

7.4 Subject Management

Subjects will be under control of the investigator or subinvestigator during the trial period. The investigator or subinvestigator will instruct the subjects to adhere to the following matters.

- To thoroughly understand the details of the administration guidance and follow it.
- To keep an administration diary every day.
- To keep a pruritus diary until the morning of the Week 1 examination (Day 7 at the latest).
- When bathing or taking a shower, to administer the IMP afterwards.
- To visit the trial site on the specified visit days during the trial period.
- To visit the trial site without morning IMP administration on the day of drug concentration measurement.
- To bring the IMP, administration diary, and pruritus diary as instructed.
- To avoid excessive exercises, getting a suntan, and excessive drinking and eating and to keep regular hours to prevent possible effects on safety.
- Information obtained during participation in this trial must not be disclosed to any third party.

8 Adverse Events

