3.3.3 Pharmacokinetics

Plasma trough concentration of OPA-15406 (trough concentration at Week 1, Week 4, and Week 8)

- 1) Plasma trough concentrations of OPA-15406 (prior to IMP administration at Week 1, Week 4, and Week 8 of IMP administration; all subjects)
- 2) Plasma concentration of OPA-15406 (prior to IMP administration and 2 hours, 4 hours, and 8 hours postdose on Day 1 and at Week 4; specific sites [target of 6 subjects from each group])
 - Pharmacokinetic parameters of OPA-15406: C_{max} , t_{max} , AUC_{0-8h} on Day 1 and at Week 4 of IMP administration
 - Accumulation of OPA-15406: Ratio of C_{max} and AUC_{0-8h} at Week 4 and on Day 1 of IMP administration

[Rationale for variable selection]

[Efficacy]

The primary variable of IGA is an indicator to assess the severity of AD and also a reliable indicator to determine the efficacy of the IMP; therefore, IGA has been established as the primary efficacy endpoint. IGA is evaluated based on the severity of overall symptoms (erythema, infiltration, papules, effusion, and scab formation) at treatment area and does not include other factors (eg, excoriation, symptoms of lichenification, severity of each part, subjective symptoms, affected BSA). Therefore, EASI, VAS and VRS for pruritus, DLQI, POEM, and affected BSA have been established as the secondary variables to evaluate the efficacy from multiple

points of view.
[Safety]
To appropriately assess the safety of this product.
[Pharmacokinetics]
To determine pharmacokinetics of OPA-15406 and the internal exposure to OPA-15406 in Japanese AD patients.

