7.1.5 Allocation of Investigational Medicinal Products to Subjects

The investigator or subinvestigator will enter the necessary information for the subject's eligibility in the IWRS. On the day of the baseline examination, the subjects confirmed to be registered in the IWRS will be allocated to the 0.3% OPA-15406 group, the 1% OPA-15406 group, or the vehicle group. The investigator or subinvestigator will confirm the allocation result and the amount of IMP to be prescribed for 2 weeks on the IWRS screen displaying the registration result, and prescribe the IMP. The weight of the dispensed IMP will be measured (unit in g; rounded to the one decimal place; same method for all subsequent IMP weight measurements hereinafter) The IMP administration will be started at the trial site after all baseline examinations are finished, and the time and date of administration will be recorded. The subjects will be instructed to visit the trial site without morning IMP administration on the day of their next visit.

**7.1.6 Baseline Examination (2 Hours, 4 Hours, and 8 Hours Postdose):
To be Conducted at Specific Trial Sites**

Application will be started within the trial site after all the baseline examinations are finished, and the source document and CRF will be recorded accordingly.

- Blood sampling for plasma drug concentration

7.1.7 Between the Day of Baseline Examination and the Day of Week 1 Examination

The investigator or subinvestigator will instruct the subject to evaluate the following item at 4 ± 2 hours, 8 ± 2 hours, and 12 ± 2 hours (if possible) after the first IMP administration on the day of the baseline examination, and then twice daily from the next day (before IMP administration in the morning and at night) up to the morning of the Week 1 examination (before administration) (up to the morning of Day 7 at the latest).

- VRS for pruritus

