7.1.8 Week 1 Examination (± 2 Days)

The investigator or subinvestigator will perform the following examinations, observations, and evaluations, and record the results in the source document and CRF.

- Physical examination
- Vital signs (including body weight)
- IGA
- EASI
- VAS for pruritus
- DLQI
- POEM
- Affected BSA
- Blood sampling for plasma drug concentration measurement
- Adverse events
- Concomitant medications and therapies
- Status of IMP administration

The investigator or subinvestigator will determine the treatment area (%) and enter it in the IWRS. Also, the investigator or subinvestigator will confirm the subject's

allocation status on the IWRS screen and, if necessary, prescribe additional IMP. When the IMP is additionally prescribed, the weight of dispensed IMP will be measured.

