 - a) Change from baseline in the total score of EASI and each symptom score at Week 1, Week 4, and Week 8
 - b) Change from baseline in VAS for pruritus at Week 1, Week 4, and Week 8
 - c) Change from baseline in the total score of DLQI at Week 1, Week 4, and Week 8
 - d) Change from baseline in the total score of POEM at Week 1, Week 4, and Week 8
 - e) Change from baseline in the total affected BSA (%) at Week 1, Week 4, and Week 8
- Change from baseline in VRS for pruritus up to Day 7
Using the OC and LOCF data sets up to Day 7, the analysis of covariance (ANCOVA) with treatment (0.3% OPA-15406, 1% OPA-15406, or vehicle) and baseline values as factors will be applied to the change from the baseline at the respective timepoints as a response variable. The least square mean will be calculated by treatment group and timepoint. Also, the difference in the least square means between the vehicle group and the respective OPA-15406 groups, the two-sided 95% confidence interval, and the p value will be calculated. Using the OC and LOCF data sets, the descriptive statistics will be calculated for measured values and changes from the baseline at the respective timepoints by treatment group and timepoint. Assessments will be made at 4, 8, and 12 hours after the start of administration, 1 day after the start of administration (morning and night), and thereafter in the same manner up to Day 7 (morning).
- Time to response in IGA and VRS
For time to response in IGA and VRS, Kaplan-Meier plots will be generated for each treatment group and vehicle group. For IGA, subjects with an IGA score of 0 (clear) or 1 (almost clear) with an improvement by at least 2 grades from the baseline are defined as responders. For VRS, subjects with VRS score of 0 (none) or 1 (mild) with an improvement by at least 1 grade from the baseline are defined as responders.

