**Table 6.4-2 Timepoints and Allowable Windows for VRS**

Timepoint	Allowable Window (Hours After the Start of IMP Administration)		
Hour 4	1	-	< 6
Hour 8	6	-	< 10
Hour 12	10	-	< 18
Hour 24	18	-	< 30
Hour 36	30	-	< 42
Hour 48	42	-	< 54
Hour 60	54	-	< 66
Hour 72	66	-	< 78
Hour 84	78	-	< 90
Hour 96	90	-	< 102
Hour 108	102	-	< 114
Hour 120	114	-	< 126
Hour 132	126	-	< 138
Hour 144	138	-	< 150
Hour 156	150	-	< 162
Hour 168	162	-	< 174

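### Ending the pruritus diary at the Week 1 visit leaves subjects seen 1 or 2 days early without the last two or four VRS timepoints that the SAP analyses

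*Protocol*

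**What the plan says.** **Collection.** Protocol 7.4 tells subjects "To keep a pruritus diary until the morning of the Week 1 examination (Day 7 at the latest". Protocol 7.1.7 and footnote i of the schedule give the same rule: readings run to the morning of the Week 1 examination, "up to the morning of Day 7 at the latest". Day 7 is thus an upper cap. Nothing asks a subject seen earlier to carry on.

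**Visit date.** Protocol 7.1.8 is headed "Week 1 Examination (± 2 Days", so a visit 2 days early is within the plan and is not a deviation.

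**Analysis.** Protocol 11.3.1.2 lists readings at 4, 8 and 12 hours, then "1 day after the start of administration (morning and night), and thereafter in the same manner up to Day 7 (morning". SAP 6.4 places each VRS reading by hours elapsed since first application. Table 6.4-2 has 16 timepoints, ending with "Hour 156 150 - < 162" and "Hour 168 162 - < 174". SAP 9.2.5 analyses VRS as it does EASI, that is by MMRM and by ANCOVA on the OC and LOCF sets. SAP 9.2.11 censors subjects without a VRS response on the day of their final VRS assessment.

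**The concern.** The SAP defines timepoints that the protocol's own stop rule prevents some compliant subjects from supplying. Whether a subject has a reading at the end of the first week then depends on the appointment date and not on anything clinical. The loss cannot be repaired after collection. It touches two listed secondary variables: change from baseline in VRS up to Day 7, and time to response in VRS. No rule in either document deals with a diary that ended because the visit came early; only the general OC, LOCF and MMRM handling applies.

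**Working it through.** **1. Reproduce the SAP grid.** After the readings at Hours 4, 8 and 12, Table 6.4-2 runs from Hour 24 to Hour 168 in 12-hour steps: (168 − 24)/12 + 1 = 13 timepoints. The protocol's schedule of morning and night for 6 days plus the morning of Day 7 gives 6 × 2 + 1 = 13. The two agree if the morning of day d after first application is Hour 24d and the night is Hour 24d + 12. The morning of Day 7 is then Hour 168 and the night of Day 6 is Hour 156. In total, 3 + 13 = 16.

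**2. Place the Week 1 visit.** SAP Table 6.4-1 puts Week 1 at Study Day 8, and the table in SAP 11.3 puts baseline at Study Day 1. The nominal visit is 8 − 1 = 7 days after first application, and ± 2 days allows 5 to 9 days after.

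**3. Apply the stop rule.** The last reading is at nominal Hour 24 × min(visit day, 7).

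| Visit, days after first application | Last reading | Timepoints lost | Left of 16 | Age of LOCF value at each lost timepoint |
|---|---|---|---|---|
| 7, 8 or 9 | Hour 168 | none | 16 | – |
| 6 | Hour 144 | 156, 168 | 14 | 12, 24 h |
| 5 | Hour 120 | 132, 144, 156, 168 | 12 | 12, 24, 36, 48 h |

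Follow-up for a subject without a VRS response shortens by 168 − 144 = 24 h or 168 − 120 = 48 h.

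**4. Check against the actual windows.** Elapsed hours = 24 × day + clock time of reading − clock time of first application. The documents give no clock times; I assume first application between 09:00 and 17:00 and morning readings between 06:00 and 08:00.

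- Visit on day 6: from 144 + 6 − 17 = 133 h to 144 + 8 − 9 = 143 h. Hour 156 opens at 150 h, so Hours 156 and 168 are always empty.
- Visit on day 5: from 120 + 6 − 17 = 109 h to 120 + 8 − 9 = 119 h. Hour 132 opens at 126 h, so Hours 132 to 168 are always empty.
- Visit on day 7 or later: from 168 + 6 − 17 = 157 h to 168 + 8 − 9 = 167 h. Hour 156 is filled. Hour 168 needs at least 162 h, so first application must be no more than 6 h later in the day than the morning reading.

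Example of the last case: first application at 14:00 and a reading at 07:00 on Day 7 give 168 + 7 − 14 = 161 h, inside the Hour 156 window. A reading at 21:00 on Day 6 gives 144 + 21 − 14 = 151 h, in the same window. SAP 6.4 keeps only the last reading in a window, so the earlier one is dropped and Hour 168 stays empty despite a complete diary.

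**5. Size.** The documents give no distribution of visit days. An even spread over the 5 permitted days would put 2/5 = 40% of subjects early. For an assumed early share of 10% to 40%, n per arm at Hour 168 falls from 60 to between 54 and 36, and the observed-case standard error rises by a factor of √(60/54) = 1.05 to √(60/36) = 1.29. The starting n of 60 supposes that everyone else fills Hour 168, which step 4 shows is not assured. The ratio depends only on the share lost, provided that early attendance is unrelated to the time of first application.

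**The case against.** The tolerance of 2 days is not a forecast, and Protocol 7.4 tells subjects to attend on the specified days. A reader might infer from the window that many subjects lose data. The documents do not support that, since the true share could be anywhere from none to all.

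A reader might also infer that nobody reaches Hours 156 and 168. For pharmacokinetics, Day 1 is the day of first application ("2 hours, 4 hours, and 8 hours postdose on Day 1 and at Week 4"). Read that way, the morning of Day 7 is only 6 days after first application, at most 143 h under the clock times assumed above. But that numbering belongs to the PK sampling. The VRS text starts its twice-daily count 1 day after the start, and it matches Table 6.4-2 only if the morning of Day 7 is Hour 168. On that count the Day 7 cap removes nothing. What remains is that the instruction to subjects leaves Day 7 undefined, which deserves one line.

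Other mitigating points stand. The MMRM draws on each subject's earlier readings, so the observed-case standard error overstates the loss in that model. SAP 9.2.11 has an explicit censoring rule. The trial is double-blind, and nothing in the documents links early attendance to treatment, so the demonstrated effect is on precision and not bias. Pruritus VAS over the preceding 24 hours is still recorded at the Week 1 visit.

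None of this removes the mismatch for a subject who attends early.

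**Conclusion.** The point holds for early attenders. A visit 1 day early empties 2 of the 16 VRS timepoints and a visit 2 days early empties 4, with no deviation by subject or site. This follows from the stop rule, the visit window and Table 6.4-2, and does not hinge on the assumed clock times within the ranges tried. How many subjects are affected is unknown, and the 5% to 29% rise in standard error rests on assumed shares of 10% to 40%. Separately, placing readings by elapsed hours can leave Hour 168 empty for on-time subjects who start in the afternoon. Protocol 11.3.7 and SAP 6.6.1 treat everything beyond the primary variable as reference analyses without multiplicity adjustment. The Week 4 IGA analysis and the sample size are not affected. The change is worth making because it is cheap and the data cannot be recovered later.

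**What to change.** **Protocol (schedule footnote i, 7.1.7 and 7.4).** Have every subject keep the pruritus diary through the morning of Day 7, defined as 7 days after the first application, whatever the date of the Week 1 visit. If that visit is early, the diary is returned at the Week 2 visit.

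**SAP (6.4 and 9.2.5).** Use the same definition of Day 7. From 1 day after first application, assign morning and night readings by scheduled day and time label instead of elapsed hours, so that an afternoon start does not leave Hour 168 empty. SAP 9.2.5 already uses the CRF time label for its separate morning and evening analysis, so the information is collected. Extending the diary without this change would still leave Hour 168 short for afternoon starters.

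**Cost.** Wording in three places in the protocol and two in the SAP, a matching change to the diary, up to 4 more entries for a subject seen 2 days early (2 if seen 1 day early), and CRF entry of those readings at the Week 2 visit. No visit is added.
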